8.5.9.3. Antibody and HARS Measurements

Blood samples for measurement of Jo-1 Ab, ADA, and serum HARS levels are to be collected according to the schedule defined in [Table 1](#). Samples will be analyzed by a central laboratory. The Week 1 Jo-1 Ab sample must be obtained and result reviewed within 2 weeks prior to the first ATYR1940 dose.

For patients with elevated ADA at the 12-week F/U visit, additional ADA testing should be performed every 1 to 3 months until the level returns to the pre-infusion baseline.

8.5.9.4. Additional Laboratory Testing and Procedures in Patients with Generalized Infusion-Related Reactions

Patients who experience generalized IRRs (see Section [7.5.5.1](#)) must have their infusion stopped and be treated as medically indicated. Vital signs, pulse oximetry, and ECGs are to be performed to gather clinical information as soon as possible after the onset of clinical symptoms of a generalized IRR (for instance, immediately after cessation of the study drug infusion if such a reaction is seen). Vital signs are to be monitored as medically indicated and pulse oximetry is to be monitored continuously for at least 2 hours after the end of infusion or until the patient has recovered, whichever is longer. ECGs should be repeated as medically indicated.

Once medical treatment of the IRR has begun, blood samples are to be obtained for assessment of:

- Plasma complement factors (C3a, C4a, C5a, Bb, and SC5b-9)
- Serum complement (CH50, C3, and C4) and trypsin

Additionally, the following tests and procedures are to be performed 1.5 to 2 hours after the onset of symptoms:

- Samples for assessment of:
 - Complete safety laboratory panel, including urine analysis and microscopy ([Section 8.5.9.1](#))
 - Plasma complement factors (C3a, C4a, C5a, Bb, and SC5b-9)
 - Serum complement (CH50, C3, and C4) and trypsin
 - Biomarkers and ATYR concentrations
- PFTs – FEV₁, FVC, FEV₁/FVC ratio, total lung capacity, DLCO

The Investigator must inform the study Medical Monitor promptly regarding any patient who experiences a generalized IRR for additional instruction.

Patients who experience generalized IRRs will continue to be monitored / have repeat assessments performed at a schedule determined by the Investigator in consultation with the Medical Monitor and Sponsor. Appropriate follow up for the patient must occur to ensure that there are no late-occurring sequelae.

8.5.10. Adverse Events

8.5.10.1. Definitions

8.5.10.1.1. Adverse Event

An AE is defined in the ICH Guideline for Good Clinical Practice as “any untoward medical occurrence in a patient or clinical investigation subject administered a pharmaceutical product and that does not necessarily have a causal relationship with this treatment” (ICH E6:1.2).

Worsening of a pre-existing medical condition, (i.e., diabetes, migraine headaches, gout) is to be considered an AE if there is either an increase in severity, frequency, or duration of the condition or an association with significantly worse outcomes.

Interventions for pretreatment conditions (i.e., elective cosmetic surgery) or medical procedures that were planned before study enrollment are not considered AEs.

In the case of death, only record “Fatal” for the event causing death. AEs that are ongoing at the end of the study or time of death are to be noted as “continuing.” Classification of AEs is to be done by the Investigator according to the NCI CTCAE, version 4.03.

The Investigator is responsible for reviewing laboratory test results and determining whether an abnormal value in an individual patient represents a significant change from baseline. In general, abnormal laboratory findings without clinical significance (based on the Investigator’s judgment) should not be recorded as AEs; however, laboratory value changes requiring therapy or adjustment in prior therapy are considered AEs.

8.5.10.1.2. Suspected Adverse Reaction

A suspected adverse reaction is any AE for which there is a reasonable possibility that the drug caused the AE. For the purposes of Investigational New Drug Application (IND) safety reporting, “reasonable possibility” and/or at least possibly related means there is evidence to suggest a causal relationship between the drug and the AE. A suspected adverse reaction implies a lesser degree of certainty about causality than adverse reaction, which means any AE caused by a drug.

8.5.10.1.3. *Serious Adverse Event*

An AE or suspected adverse reaction is considered “serious” if, in the view of either the Investigator or Sponsor, it results in any of the following outcomes:

- is fatal
- is life-threatening (i.e., places the patient at immediate risk of death)
- requires in-patient hospitalization or prolongation of existing hospitalization
- results in persistent or significant disability/incapacity
- is a congenital anomaly/birth defect
- Is an important medical event. An important medical event is an event that may not result in death, be life-threatening, or require hospitalization but may be considered an SAE when, based upon appropriate medical judgment, it may jeopardize the patient and may require medical or surgical intervention to prevent one of the outcomes listed in the definitions for SAEs. Examples of such medical events include allergic bronchospasm requiring intensive treatment in an emergency room or at home, blood dyscrasias or convulsions that do not result in inpatient hospitalization, or the development of drug dependency or drug abuse.

A hospitalization meeting the regulatory definition for “serious” is any inpatient hospital admission that includes a minimum of an overnight stay in a health care facility. Any AE that does not meet one of the definitions of serious (i.e., emergency room visit, out-patient surgery, or requires urgent investigation) may be considered by the Investigator to meet the “important medical event” criterion for classification as an SAE.

8.5.10.1.4. *Unexpected Adverse Event*

An AE or suspected adverse reaction is considered “unexpected” if it is not listed in the Investigator’s Brochure or is not listed at the specificity or severity that has been observed; or, if an Investigator’s Brochure is not required or available, is not consistent with the risk information described in the General Investigational Plan or elsewhere in the current application, as amended.

8.5.10.1.5. *Serious and Unexpected Suspected Adverse Reaction*

A suspected unexpected serious adverse reaction (SUSAR) is any event that meets all 3 of the following definitions:

- 1) suspected adverse reaction (Section 8.5.10.1.2);
- 2) serious (Section 8.5.10.1.3); and
- 3) unexpected (Section 8.5.10.1.4).

8.5.10.2. Adverse Event Assessment

All AEs will be collected and recorded in this study from the time of the first ATYR1940 dose in this study through the EOS visit, or after the end of the study, if thought to be related to study drug. (AEs occurring through 30 days after the last study drug dose in the parent study and those occurring >30 days after the last study drug dose in the parent study that are considered by the Investigator to be study drug-related are to be reported in the parent study.) This includes AEs the patient reports spontaneously, those observed by the Investigator, and those elicited by the Investigator in response to open-ended questions during scheduled study center visits. Furthermore, all AEs that presented in the parent study that are ongoing at Week 1 in the current study will be recorded as such.

Each AE is to be assessed by the Investigator with regard to the following categories.

Serious/Non-Serious

AEs that meet the criteria specified in Section [8.5.10.1.3](#) are to be considered serious.

Relationship to Study Drug

The relationship of each AE to ATYR1940 is to be assessed by the Investigator according to categories in [Table 8](#).

Table 8: Criteria for Determination of Adverse Event Relationship to Study Drug

AE (is):	Relationship between ATYR1940 and AE:				
	Category				
	None	Unlikely	Possibly	Likely	Definitely
Clearly the result of an external factor	Yes	No	No	No	No
Probably/possibly the result of another factor	No	Yes	Yes	No	No
Has a chronological relationship with the time of administration and/or represents a known reaction to Study Drug	No	No	Yes	Yes	Yes
Disappears or decreases after discontinuation of the Study Drug	NA	NA	NA	Yes	Yes
Recurr on renewed administration (re-challenge)	No	No	NA	NA	Yes or NA**

** A re-challenge is not required; if done, re-challenge would be expected to be positive.

NA Not applicable

Intensity

The intensity of each AE is to be assessed by the Investigator according to the NCI CTCAE, version 4.03. If the AE is not included in the NCI CTCAE, version 4.03, then the Investigator is to determine the intensity of the AE according to the following criteria:

- Mild (Grade 1): Asymptomatic or mild symptoms: clinical or diagnostic observations only; intervention not indicated.
- Moderate (Grade 2): Minimal, local, or non-invasive intervention indicated; limiting age-appropriate instrumental activities of daily living.
- Severe (Grade 3): Severe or medically significant but not immediately life threatening; hospitalization or prolongation of hospitalization indicated; disabling; limiting self-care activities of daily living; incapacitating with inability to work or perform normal daily activity.
- Life-threatening (Grade 4): consequences: urgent intervention indicated.
- Death (Grade 5) related to an AE.

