8.5.10.3. Recording Adverse Events

All AEs occurring from the time written informed consent is obtained through the EOS visit are to be recorded in the source documents and in the eCRF. All AE reports are to contain the following details regarding the AE: a brief description, onset date and time,

resolution date and time, intensity, treatment required, relationship to ATYR1940, ATYR1940 action taken, outcome, and whether the event is classified as serious.

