8.5.10.4. Reporting Serious Adverse Events

SAEs will be collected and recorded throughout the study period, beginning with the signing of the ICF through the EOS visit, or after the end of the study if thought to be related to ATYR1940.

The Investigator must report all SAEs within 24 hours of discovery to:

[REDACTED]
Email: [REDACTED]
Telephone number: [REDACTED]

A completed SAE report is to be sent to the Medical Monitor's attention within 24 hours of discovering the event. The initial report should include at least the following information:

- Patient's ID number;
- Description and date of the event;
- Criterion for serious; and
- Preliminary assignment of causality to ATYR1940.

The Medical Monitor will contact the Investigator via telephone for follow-up information regarding the SAE, as appropriate.

The Investigator, or designated party, should notify the appropriate IRB/EC of SAEs occurring at the study center and other AE reports received from aTyr, in accordance with local procedures and statutes.

SAEs that are considered as possible or probably related to the investigational product, and as unexpected (i.e., SUSARs), will be reported to the concerned Competent Authorities (CAs) and IRBs/ECs by the Sponsor or Sponsor's designee as required by applicable local regulations. Per regulation, any fatal or life-threatening SUSAR will be reported to the CAs/IRBs/ECs within 7 calendar days, and additional information within an additional 8 calendar days. The Sponsor or Sponsor's designee is required to submit any other SUSAR to the CAs/IRBs/ECs within 15 calendar days of notification. The Sponsor or its designee is also responsible for notifying the investigational sites of all expedited SAEs. The Investigator must keep copies of all expedited SAE information including correspondence with the Sponsor on file.

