9.6 Safety, Tolerability, and Immunogenicity Analyses

9.6.1 Adverse Events, Serious Adverse Events, and Deaths

Adverse events will be collected beginning at informed consent until the end of the study. See Section 6 for definition of TEAE. Adverse events will be coded using MedDRA to assign an SOC and PT to each adverse event and TEAEs will be summarized.

An overall summary of TEAEs including the following categories will be presented for the Safety analysis set by disease group:

- Number of TEAEs reported
- Number and percentage of patients reporting at least one TEAE
- Number and percentage of patients with at least one related TEAE (see definition in Section 6)
- Number and percentage of patients with at least one TEAE leading to study medication withdrawal
- Number and percentage of patients with at least one serious TEAE
- Number of patients with at least one TEAE with fatal outcome

The number and percentage of patients reporting TEAEs will also be summarized for the categories below. Counts will be by patient, not event, and patients will only be counted once within each SOC or PT. Tabulations will be sorted by descending frequency of the number of patients reporting the TEAE for each SOC and by PT within each SOC. Additionally, patients with multiple events within a particular SOC or PT will be counted under the category of their most severe event within an SOC or PT for summaries by maximum grade. Summaries to be provided are the following:

- TEAEs by MedDRA PT
- TEAEs by MedDRA SOC and PT

- Related TEAEs by MedDRA SOC and PT
- TEAEs by MedDRA SOC, PT, and maximum CTCAE grade
- SAEs by MedDRA SOC and PT
- TEAEs leading to study medication withdrawal by MedDRA SOC and PT
- TEAEs with a fatal outcome by MedDRA SOC and PT

TEAEs and non-TEAEs will be listed together.

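### Protocol 8.5.10.2 assigns the same adverse events to both the parent study and 006, so an event may be entered twice or be missing from the 006 database

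*Protocol*

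**What the plan says.** Protocol 8.5.10.2 opens with an inclusive rule: "All AEs will be collected and recorded in this study from the time of the first ATYR1940 dose in this study". A parenthesis follows that sends two groups of events to the parent study. The first group, whatever the cause, is "AEs occurring through 30 days after the last study drug dose in the parent study". The second group is made up of later events, namely any with onset ">30 days after the last study drug dose in the parent study that are considered by the Investigator to be study drug-related". No stop date is given for this second group. The section then adds that "all AEs that presented in the parent study that are ongoing at Week 1 in the current study will be recorded as such", without saying whether this creates a new 006 record or marks a continuation of the parent record.

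Other sections start the clock elsewhere:

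- Protocol 8.5.10.3: "All AEs occurring from the time written informed consent is obtained through the EOS visit".
- Protocol 8.5.10.4, for SAEs: "beginning with the signing of the ICF through the EOS visit".
- SAP 9.6.1: "Adverse events will be collected beginning at informed consent until the end of the study".

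SAP 5.2 pools parent and 006 data in the Safety Population Cumulative, and the AE tables run on that population. Table 14.2.1.1 reports a number of events, not only patients, in a parent-plus-current block and again in a current-study block. Listing 16.2.9 takes in all AEs from both studies. SAP Section 6 defines a current-study TEAE by onset on or after the parent Week 13 visit (Week 13 Day 3 for study 004). Neither document gives a rule for matching an event held in both databases.

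**The concern.** Safety is the first objective, up to 24 patients are expected and the analysis is descriptive, so the AE tables and listings are the main result. A site with a rollover patient who has an AE in the second week of 006 finds one sentence placing it in 006 and the next placing it in the parent study. For a drug-related AE the conflict never ends.

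At stake are the event counts, the AE listings (including those supplied to the Data Monitoring Board about every 3 months) and the completeness of the 006 safety record. SAP 1.1 shows that overlap at the transfer visit was noticed for other data: it drops repeat collection of complement, tryptase, visual acuity and audiometry because the parent study already collects them. It does not address AEs.

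**Working it through.** The documents give no AE count or rate, so there is no plan figure to reproduce. The check is date arithmetic, then a trace into the planned outputs.

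**Inputs**

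- Parent window for any AE: 30 days after the last parent dose (Protocol 8.5.10.2).
- Gap from last parent dose to first 006 dose: 7 days ideal, 21 days maximum, longer only case by case (Protocol 4.1).
- 006 dosing: weekly (Protocol 7.5.3).

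**1. Length of the overlap.** Overlap = max(0, 30 − gap), in elapsed days.

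| Gap (days) | Overlap, any AE | 006 doses inside it (days after last parent dose) |
|---|---|---|
| 7 | 30 − 7 = 23 | 4 (days 7, 14, 21, 28) |
| 21 | 30 − 21 = 9 | 2 (days 21, 28) |
| 30 or more | 0 | not applicable |

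Counting both end days adds one day (24 and 10). Zero overlap needs the case-by-case exception. For related AEs there is no upper limit at any gap.

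**2. The two readings of 8.5.10.2.**

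- Both sentences apply: an AE in the overlap, or any later related AE, is due in both databases.
- The parenthesis is an exception: the AE goes to the parent study only. The opening sentence is then untrue for the first 9 to 23 days of 006 dosing and for every related AE afterwards, and those events leave the 006 database.

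**3. Effect on outputs.** Take one event held in both databases. Stacked, it counts as 2 events; matched, as 1. The number of patients is 1 either way. Under SAP 9.6.1 each patient counts once within a system organ class or preferred term, so n (%) is unchanged. What moves is the Number of TEAEs row in Table 14.2.1.1, plus repeated lines in the AE listings. Because SAP Section 6 works by onset date, both copies could also qualify for the current-study block.

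**4. Illustrative size of inflation.** Assumptions not in the documents: a uniform AE rate, 12 to 48 weekly doses in 006, and every eligible event entered twice. Parent first-to-last dose is taken as Week 2 to Week 13, (13 − 2) × 7 = 77 days, and follow-up as 84 days.

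Total days = 77 + gap + 7 × (T − 1) + 84, where T is weeks in 006. Inflation from the 30-day clause = overlap / total.

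- Gap 7: T = 12 gives 23/245 = 9.4%; T = 48 gives 23/497 = 4.6%.
- Gap 21: T = 12 gives 9/259 = 3.5%; T = 48 gives 9/511 = 1.8%.

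Now add the drug-related clause, with a share q of later AEs judged related (assumed 10% to 30%): inflation = (overlap + q × remaining 006 days) / total.

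- Lowest: gap 21, T = 12, q = 0.1: (9 + 0.1 × 152)/259 = 9.3%.
- Highest: gap 7, T = 48, q = 0.3: (23 + 0.3 × 390)/497 = 28.2%.

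These are upper-end figures, because they assume that every eligible event is duplicated.

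**The case against.** The strongest reply is that the parenthesis is an allocation rule: it gives each event one home, and nothing tells a site to enter an event twice. That is fair. A reader might infer that double counting will happen; the documents do not support that. Whether parent AE pages stay open after transfer depends on parent protocols and data-management plans that are not available here. But the allocation reading does not rescue the text, because it takes early and related events out of the 006 record.

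Four narrower points also stand:

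- A reader might infer that ongoing parent AEs are entered again as new events. The section says only that they are recorded as ongoing.
- A reader might infer that the parent/current split of the TEAE tables depends on which sentence a site followed. SAP Section 6 largely answers this: it sets the current-study window by onset date, and the tables run on pooled data.
- The first-dose versus consent difference is probably short in most cases, since the Schedule of Events places consent in the Week 1 column.
- Duplicates should often be visible. Listing 16.2.9 shows onset, stop and source study, sorted by patient and start date, and SAP 8.4 has output reviewed before lock. That is a useful control, but not a rule for deciding which record counts.

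**Conclusion.** The point holds as a faulty stated rule that should be corrected. Protocol 8.5.10.2 claims the same AEs for two studies, for 23 to 9 days at the standard gaps and indefinitely for drug-related AEs. The start of 006 recording is also stated two ways.

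The consequence is bounded. If events are entered twice, the Number of TEAEs rows and the AE listings are affected. If the parenthesis is read as exclusive, early and related events may be missing from the 006 database. It would be tempting to conclude that AE incidence percentages are inflated; they are not, because patients are counted once. The window lengths rest only on the documents. The inflation percentages are illustrations under stated assumptions and should not be read as estimates.

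**What to change.** 1. In Protocol 8.5.10.2, state one owning study per AE: onset before the first 006 dose belongs to the parent study, onset on or after it to 006. Limit the 30-day and drug-related parent clauses to patients who have not started 006 dosing.
2. Align Protocol 8.5.10.3, Protocol 8.5.10.4 and SAP 9.6.1 with that rule. Include SAP Section 6, whose TEAE window opens at parent Week 13 and would otherwise conflict with it.
3. Link AEs ongoing at transfer to the parent record, so that they are not counted as new events.
4. Before event counts are produced, flag candidate duplicates across the databases by linked patient ID (patients are renumbered under Protocol 6.1), preferred term and reported onset date and time. Do not use imputed dates: SAP Appendix 2 sets many partial start dates to the first 006 dose, so distinct events can share one. Review the flags by hand, since automatic deletion could merge genuine separate same-day events.

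The cost is minor wording changes and a small reconciliation step. Design, visits and sample size are untouched.

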8.5.10.3. Recording Adverse Events

All AEs occurring from the time written informed consent is obtained through the EOS visit are to be recorded in the source documents and in the eCRF. All AE reports are to contain the following details regarding the AE: a brief description, onset date and time,

resolution date and time, intensity, treatment required, relationship to ATYR1940, ATYR1940 action taken, outcome, and whether the event is classified as serious.

8.5.10.4. Reporting Serious Adverse Events

SAEs will be collected and recorded throughout the study period, beginning with the signing of the ICF through the EOS visit, or after the end of the study if thought to be related to ATYR1940.

The Investigator must report all SAEs within 24 hours of discovery to:

[REDACTED]
Email: [REDACTED]
Telephone number: [REDACTED]

A completed SAE report is to be sent to the Medical Monitor's attention within 24 hours of discovering the event. The initial report should include at least the following information:

- Patient's ID number;
- Description and date of the event;
- Criterion for serious; and
- Preliminary assignment of causality to ATYR1940.

The Medical Monitor will contact the Investigator via telephone for follow-up information regarding the SAE, as appropriate.

The Investigator, or designated party, should notify the appropriate IRB/EC of SAEs occurring at the study center and other AE reports received from aTyr, in accordance with local procedures and statutes.

SAEs that are considered as possible or probably related to the investigational product, and as unexpected (i.e., SUSARs), will be reported to the concerned Competent Authorities (CAs) and IRBs/ECs by the Sponsor or Sponsor's designee as required by applicable local regulations. Per regulation, any fatal or life-threatening SUSAR will be reported to the CAs/IRBs/ECs within 7 calendar days, and additional information within an additional 8 calendar days. The Sponsor or Sponsor's designee is required to submit any other SUSAR to the CAs/IRBs/ECs within 15 calendar days of notification. The Sponsor or its designee is also responsible for notifying the investigational sites of all expedited SAEs. The Investigator must keep copies of all expedited SAE information including correspondence with the Sponsor on file.

